4.6.2 Double-Blind Exclusion Criteria

- 1. Patients currently receiving anticancer therapies or who have received anticancer therapies within 4 weeks of the start of Everolimus (including chemotherapy, radiation therapy, antibody based therapy, etc.);
- Known intolerance or hypersensitivity to Everolimus or other rapamycin analogs (e.g. sirolimus, temsirolimus);
- 3. Known impairment of gastrointestinal (GI) function or GI disease that may significantly alter the absorption of oral Everolimus;

- 4. Uncontrolled diabetes mellitus as defined by HbA1c > 8% despite adequate therapy. Patients with a known history of impaired fasting glucose or diabetes mellitus (DM) may be included, however blood glucose and antidiabetic treatment must be monitored closely throughout the trial and adjusted as necessary;
- 5. Patient with uncontrolled hyperlipidemia: fasting serum cholesterol > 300 mg/dL OR > 7.75 mmol/L AND fasting triglycerides > 2.5 x ULN.
- 6. Patients who have any severe and/or uncontrolled medical or psychiatric conditions such as:
 - a. Unstable angina pectoris, symptomatic congestive heart failure, myocardial infarction ≤6 months prior to start of Everolimus, serious uncontrolled cardiac arrhythmia, or any other clinically significant cardiac disease
 - b. Symptomatic congestive heart failure of New York heart Association Class III or IV
 - Active (acute or chronic) or uncontrolled severe infection, liver disease such as cirrhosis, decompensated liver disease, and active and chronic hepatitis (i.e. quantifiable HBV-DNA and/or positive HbsAg, quantifiable HCV-RNA),
 - d. Known severely impaired lung function (spirometry and DLCO 50% or less of normal and O_2 saturation 88% or less at rest on room air)
 - e. Active, bleeding diathesis;
 - f. unstable angina pectoris, symptomatic congestive heart failure, myocardial infarction ≤6 months prior to start of Everolimus, serious uncontrolled cardiac arrhythmia, or any other clinically significant cardiac disease
 - g. Symptomatic congestive heart failure of New York Heart Association Class III or lactive (acute or chronic) or uncontrolled severe infection, liver disease such as cirrhosis, decompensated liver disease, and active and chronic hepatitis (i.e. quantifiable HBV-DNA and/or positive HbsAg, quantifiable HCV-RNA),
 - h. known severely impaired lung function (spirometry and DLCO 50% or less of normal and O_2 saturation 88% or less at rest on room air),
 - i. severe psychiatric disorders, such as bipolar disorders or schizophrenia,
 - j. active substance-abuse,
 - k. active, bleeding diathesis;
- 7. Chronic treatment with corticosteroids or other immunosuppressive agents. Topical or inhaled corticosteroids are allowed;
- 8. Known history of or seropositivity for Hepatitis B, Hepatitis C, or HIV
- Patients who have received live attenuated vaccines within 1 week of start of Everolimus and during the study. Patient should also avoid close contact with others who have received live attenuated vaccines. Examples of live attenuated vaccines include intranasal influenza, measles, mumps, rubella, oral polio, BCG, yellow fever, varicella and TY21a typhoid vaccines;
- 10. Patients who have a history of another primary malignancy, with the exceptions of:
 - a. non-melanoma skin cancer
 - b. carcinoma in situ of the cervix, uteri, or breast from which the patient has been disease free for ≥3 years;
- 11. Planned changes to concomitant medications;
- 12. Prior or concomitant therapy with known or possible anti-mTOR activity, including rapamycin (sirolimus);
- 13. Concomitant therapy with strong inhibitor (e.g., cyclosporine and ketoconazole) or inducer of CYP3A;
- 14. Active infection at time of enrollment;
- 15. Patients with a history of non-compliance to medical regimens or who are considered potentially unreliable or will not be able to complete the entire study;
- 16. Patients who are currently part of or have participated in any clinical investigation with an investigational drug within 1 month prior to dosing;
- 17. Pregnant or nursing (lactating) women;
- 18. Women of child-bearing potential (WOCBP), defined as all women physiologically capable of becoming pregnant, must use highly effective methods of contraception during the study and 8 weeks after. Highly effective contraception methods include:
 - a. A combination of any two of the following:
 - i. Use of oral, injected or implanted hormonal non-estrogen containing methods of contraception or;
 - ii. Placement of an intrauterine device (IUD) or intrauterine system (IUS);
 - iii. Barrier methods of contraception: condom or occlusive cap (diaphragm or cervical/vault caps) with spermicidal foam/gel/film/cream/ vaginal suppository;
 - b. Total abstinence or;

c. Male/female sterilization.

Women are considered post-menopausal and not of child-bearing potential if they have had 12 months or natural (spontaneous) amenorrhea with an appropriate clinical profile (e.g. age appropriate, history of vasomotor symptoms) or have had surgical bilateral oophorectomy (with or without hysterectomy) or tubal ligation at least six weeks prior to randomization. In the case of oophorectomy alone, only when the reproductive status of the woman has been confirmed by follow up hormone level assessment is she considered not of child-bearing potential.

Version Date: 05Feb20

- 19. Male patients whose sexual partner(s) are WOCBP who are not willing to use adequate contraception, during the study and for 8 weeks after the end of treatment
- 20. Major surgery, radiation therapy or stereotactic radio-surgery within previous 4 weeks at time of screening
- 21. Neurosurgery within prior 6 months at time of screening.

4.6.3 Open-Label Phase Inclusion Criteria

- 1. Patients who completed Double-Blind phase of the study and were assigned to the placebo treatment arm;
- 2. Verbal consent (and assent, as appropriate) obtained prior to any open-label phase study procedures.

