4.3 Blinded Treatment Phase

All baseline procedures and evaluations should be completed within 6 weeks of the screening visit. If a patient's safety lab results are out of range, and the investigator has reason to believe there were situational factors affecting the values, the screening labs may be repeated. The safety evaluations may be completed at a lab that is geographically close to the participant and either provide the results of that analysis directly to the study team, or a sign a release so the study team can obtain the results from the lab. If a patient's baseline visit is more than 6 weeks after the screening visit the participant must have the safety labs re-drawn and processed, have the physical and neurological exam re-done, and the study team will confirm that there are no changes in the medical history or changes to the patient's current medications. If the screening safety evaluation and/or lab results are out-of-range, the participant will not be eligible to participate in the study. Patients who meet the study eligibility criteria following screening will be randomized to receive everolimus or placebo. The randomization ratio is 1:1, with one patient being randomly assigned to everolimus for every one patient randomly assigned to placebo. Treatment assignment via the RDCRN Members' Website should occur prior to the Baseline visit to allow adequate time for pharmacy preparation. Patients must start treatment within 7 days of the baseline visit, given that the participant still meets all inclusionary criteria and has not developed any exclusionary criteria. The medication should be taken at the same each day with a light, low-fat breakfast (i.e. 8:00 am with light breakfast).

The duration of blinded phase this study is 6 months. Patients will have their first daily dose of everolimus or placebo within 7 days of Visit 2 (baseline) and will continue on treatment for 6 months unless an intolerable toxicity occurs, withdrawal of consent, or investigator decision to discontinue the patient from study treatment.

Starting dose and adjustments are defined in Section. 6.2.

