4.4 Open Label Phase

Individuals in the placebo group will be invited to enter the 6-month open-label extension trial that will follow the same schedule as the blinded treatment phase. The final visit, or the Month 6 visit, in the blinded treatment phase will serve as the baseline visit of the open label phase if the participant chooses to enter the open label phase. Safety labs obtained at the end of the blinded phase will be used as baseline safety labs for the open-label phase. Similarly, the scores from the patient's developmental assessments will be used as both the 6-month blinded treatment phase data, and the baseline open-label phase data. Study staff should be prepared to dispense open label medication at this visit. If the patient is unable to enter the open-label phase at the final visit of the blinded treatment phase, the patient can come back within 2 weeks (+/- 2 weeks) of this visit date. Treatment, assessments, and outcomes of the open-label phase will also be identical to the double-blind phase.

The next visit will be the Month 1 visit. A PK sample, as well as specified safety labs, will be drawn on site and sent to LabConnect LLC. If the participant receives a dose adjustment at the time of this visit, study staff will work with the participant/family to get another sample taken at the study site or locally by a trained phlebotomist. The Month 3 visit and the Month 6 visit will include safety labs, developmental testing, optional EEG/AEP and eye tracking procedures, physical and neurological exams, vital signs, and other study questionnaires. A PK sample may also be collected from a patient experiencing an adverse event or side effect. The decision to obtain this sample will be made by the site physician.

The Month 2, Month 4, and Month 5 visits can be in person or by-phone if that is preferred by the family. If performed by phone, a phone interview will be performed to collect safety and other data, review AEs, and assess changes in mood or behavior. All applicable CRFs will be completed.

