7.6 Double-Blind Treatment Assignment Unblinding

Prior to the Month 6 visit or early termination, the site will obtain the unblinded treatment assignment via the procedures described in the 7904 Manual of Procedures. At the conclusion of the double-blind phase or early termination, the blind will be broken immediately. Individuals on the active drug will exit the study, and those who were on placebo will be invited to join the open label phase (section 4.4).

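### For placebo patients the first open-label dose is their first everolimus, yet neither 4.6.3 nor 4.4 requires a current negative pregnancy result or review of the Month 6 safety labs before it

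*Combined protocol and SAP*

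**What the plan says.** Section 4.6.3 gives the open-label phase its own list of two items. The first is "Patients who completed Double-Blind phase of the study and were assigned to the placebo treatment arm"; the second is verbal consent or assent. Neither is a laboratory or pregnancy criterion.

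Section 4.4 makes the last blinded visit the open-label baseline visit. It says "Safety labs obtained at the end of the blinded phase will be used as baseline safety labs for the open-label phase" and "Study staff should be prepared to dispense open label medication at this visit". A patient who cannot start then may return later: "the patient can come back within 2 weeks (+/- 2 weeks) of this visit date". Section 7.6 makes same-day dispensing practical: "Prior to the Month 6 visit or early termination, the site will obtain the unblinded treatment assignment". Blood samples go to a central laboratory (sections 4.3 and 7.15), with no turnaround time given.

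On pregnancy, inclusion criterion 10 in section 4.6.1 ties the negative serum test to screening. Section 7.16.4 repeats the serum test at Month 6 and allows urine tests at on-site visits when judged clinically necessary.

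Entry to the blinded phase is handled differently. Section 4.2 requires the screening assessments to be evaluated before randomization. Under section 4.3, if the baseline visit "is more than 6 weeks after the screening visit the participant must have the safety labs re-drawn and processed".

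**The concern.** These patients have taken only placebo for six months, so open-label entry is a first exposure in the same sense as the start of the blinded phase. Blinded entry has an explicit step at which results are read before the patient goes forward. Open-label entry has none in the text.

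A site could therefore follow the protocol exactly and still start everolimus in a woman who became pregnant after screening, or in a patient whose marrow, liver or renal values have left the entry limits, before the Month 6 result is seen. Inclusion 10 itself says that fetal effects at these doses are not known. The contraception rules make a pregnancy less likely but do not detect one, and a later hold cannot undo a fetal exposure. The laboratory part matters less, because the dose-hold rules in Table 4 act once results return.

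**Working it through.** **Step 1. Does any text require a result in hand before the first open-label dose?**

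| Text | What it gives | What it leaves open |
|---|---|---|
| 4.6, opening paragraph | Criteria must still be met at the baseline visit and apply to all patients unless otherwise specified | The results it requires to be reviewed are those of the screening evaluations |
| 4.3, start of treatment: "Patients must start treatment within 7 days of the baseline visit, given that the participant still meets all inclusionary criteria"; the sentence goes on to require that no exclusion has arisen since. Read with 4.4: "Treatment, assessments, and outcomes of the open-label phase will also be identical to the double-blind phase" | A plausible route by which a new pregnancy (exclusion 17) bars open-label entry | States a condition, not a test result that must be seen |
| Table 13B, Visit 9 eligibility check, with 7.21 | A fresh check; no entry if the phase's criteria are unmet | Does not say that Month 6 results must be back; the list written for this phase is 4.6.3 |
| Table 13B footnote | Baseline procedures may be carried over only within 2 weeks of the Month 6 visit | Limits the age of the procedure, not whether its result has been read |
| 7.16.4 | Serum pregnancy test at Month 6 | Not a condition of dosing; urine tests are optional |

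None of the five does.

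**Step 2. How old is the latest required result if Month 6 results are pending?**

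Inputs: one month = 365.25/12 = 30.44 days (convention); visit windows of ±14 days and baseline within 42 days of screening (Table 13A).

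- Safety labs, Month 3 to Month 6: 3 × 30.44 = 91.3 days. With both windows, 91.3 − 28 = 63 days to 91.3 + 28 = 119 days.
- Required pregnancy test, screening to Month 6: 6 × 30.44 = 182.6 days from baseline. Minimum 182.6 − 14 + 0 = 169 days; maximum 182.6 + 14 + 42 = 239 days.

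For comparison, at the blinded baseline visit the screening labs are at most 42 days old, or they are re-drawn.

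**Step 3. How many patients?**

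40 randomized 1:1 gives 40 × 1/2 = 20 on placebo. At the 10% dropout in section 17.1, 20 × 0.9 = 18. The number of women of child-bearing potential is not stated.

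**Step 4. How many doses could precede review?**

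With results back T days after the visit and the first dose d days after it, once-daily dosing gives max(0, T − d) doses before review. The documents do not give T. If T is assumed to lie between 0 and 7 days, a first dose on the day of the visit (d = 0) gives 0 to 7 doses, and a first dose on day 7 gives none. The answer is also zero if the Month 6 blood is drawn early enough within its window.

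**The case against.** The strongest reply is that the protocol already bars a pregnant woman from starting open-label drug. The 4.3 condition on starting treatment covers exclusions that have newly arisen. Section 4.4 makes open-label treatment the same as blinded treatment. Table 13B calls for an inclusion and exclusion check at Visit 9, and since 4.6.3 contains no exclusions, that check is arguably empty unless those in 4.6.2 apply. This is a fair reading, and it disposes of one inference a reader might draw, that pregnant or out-of-range patients are eligible for the open-label phase. The documents do not establish that. What remains is that eligibility could be confirmed from screening and Month 3 data without any current result.

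A second tempting inference is that Month 6 testing is missing, or that drug will be given before results are known. Neither is supported. Both tests are scheduled. Being ready to dispense is not an order to dispense, section 4.4 allows a later return, and the Pharmacy Manual, which governs dispensing under section 7.5, is not among the documents and may contain a check.

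A third reply is that the laboratory half has little consequence. Placebo patients have had labs at Months 1 and 3, out-of-range values prompt a physician's assessment (section 4.3), and Table 4 holds drug for neutrophils below 1,000/mm³ (the entry limit) and platelets below 75,000/mm³ (entry limit 80,000/mm³). This largely stands and makes that half secondary. It does not answer the pregnancy half.

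**Conclusion.** The point holds as a minor gap in what the protocol requires. No text makes a current negative pregnancy result, or review of the Month 6 labs, a condition of the first open-label dose, although evaluation is required before randomization into the blinded phase. Pregnancy exposure is the main risk and falls on an uncounted subset of at most 20 patients, all of whom must use contraception.

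The ages in the working apply only if Month 6 results are still pending at the visit, and the upper pregnancy figure assumes a baseline visit within 42 days of screening. How many unreviewed doses would follow cannot be determined from the documents. The conclusion also rests on the protocol text alone: a check in the Pharmacy Manual would reduce the practical risk, though a participant-safety condition of this kind belongs in the protocol.

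**What to change.** - **4.6.3:** require a negative urine pregnancy test on the day of open-label dispensing for women of child-bearing potential. Section 7.16.4 already permits this test.
- **4.4:** state that the first open-label dose is taken only after the investigator has reviewed the Month 6 marrow, liver and renal results against inclusion limits 5 to 7. Drug may be dispensed at the visit, with the start held until the site confirms.
- **Late entrants:** if open-label entry is more than 2 weeks after Month 6, repeat the labs. The return visit in 4.4 can fall up to 2 + 2 = 4 weeks later, beyond the 2-week carry-over in the Table 13B footnote.
- **Early blood draw:** if sites draw the Month 6 labs ahead of the visit, within the ±14-day window and off site where needed (7.15), do so in both arms. Drawing early only in placebo patients would reveal assignment before the Month 6 assessments.

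The cost is protocol wording, one urine test per woman of child-bearing potential, a possible short delay to open-label start, occasional repeat labs for late entrants, and a separate blood-draw appointment where the early draw is used. The Month 6 blood tests themselves are already collected.

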4.6.4 Screening for Hepatitis B, Hepatitis C, and HIV

Study teams will review a list of risk factors for Hepatitis B, Hepatitis C, and HIV with participants/families. If the participant meets any of these risk factors, a serology blood sample will be drawn at the screening visit. If the participant is positive for any of the viruses, they will be ineligible to participate in the study.

Patients that meet any of the risk factors below will have a blood sample drawn for a serology panel that will test for Hepatitis B (HBV-DNA, HBsAg, HBs Ab, and HBc Ab), Hepatitis C (quantitative RNA-PCR and HCV Ab), and HIV (HIV I/II).

- Currently live or have lived in Asia, Africa, Central and South America, Eastern Europe, Spain, Portugal, and Greece
- Had an operation in a developing country at any time
- Received a blood transfusion prior to 1990
- Are current or past IV drug user
- Have body piercing or tattoos
- Have a biological mother diagnosed with HIV
- Have a biological mother diagnosed with hepatitis B or hepatitis C
- Have a history of hepatitis B infection (e.g., dark urine, jaundice, right upper quadrant pain) or hepatitis
- Have had household contact with hepatitis B or hepatitis C infected patient(s)
- Have current or prior high-risk sexual activity
- Have current or prior dialysis

Hepatitis B, Hepatitis C, and HIV screening will be done at the discretion of the principal investigator at each site, using these factors. If a patient tests positive for HIV, the Principal Investigator at each enrolling site is responsible for reporting the result to the appropriate public health agency based on IRB and state regulations. The Principal Investigator will inform the patient or parent of the positive result and reporting plan. Patients that screen positive for HIV will be provided counseling.

4.6.5 Columbia Suicide Severity Rating Scale (C-SSRS)

In light of the recent evidence linking psychotropic medications to suicidal behaviors, it is important to closely monitor the mental well-being of patients taking medications that target the central nervous system⁶¹. Therefore, assessment of suicidal ideation/behaviors will be completed during the screening phase and will be monitored during the trial. The C-SSRS will be administered to assess the presence of suicidality throughout the entirety of the trial.

The Columbia-Suicide Severity Rating Scale (C-SSRS) is an interview that prospectively assesses suicidal ideation and behavior using a semi-structured interview to probe patient responses. The C-SSRS is intended to

be used by individuals who have received training in its administration. Ultimately, the determination of the presence of suicidal ideation and/or behavior depends on the judgment of the individual administering the scale.

A trained investigator will administer the C-SSRS. Patients 13 years of age and older will complete the scale for themselves. Parents/caregivers will complete the interview for patients that are under the age of 13, or for patients unable to understand and complete the assessment due to cognitive impairment. Additionally, the study physician will proactively assess patients for suicidality and mood disturbances through discussions with the patient and/or parent. Any positive responses will be further investigated, and appropriate medical treatment will be initiated.

The C-SSRS will be completed at screening, Month 1, Month 3 and Month 6 of the blinded phase, and Month1, Month 3 and Month 6 of the open label phase. For the screening visit, the C-SSRS will be evaluate the last 12 months. For Month 1, Month 3, and Month 6 of the double-blind and open-label phases, the C-SSRS will assess any changes from the previous visit. If, at any assessment, the Suicidal Ideation (questions #1-5) score is a 4 or above, or the patient (or parents) answers "yes" to any Suicidal Behavior item (actual attempt, interrupted attempt, aborted attempt, preparatory acts or behavior, or suicidal behavior), the patient must be referred to a health care professional for further assessment and/or treatment. If the participant meets any of these criteria at the screening visit, they will be excluded from the study. Once the participant has started study medication, the decision about whether the participant should be withdrawn from study treatment will be determined by the site PI, in collaboration with one of the site's mental health professionals and [name]. To note, any study investigator or research staff can refer a participant to the designated site mental health professional for any concerns about suicidality, even if the patient does not meet the criteria detailed above.

The patient should not be allowed to leave the study center until the results of the C-SSRS are reviewed and the patient is not considered to be at risk. If there is doubt about whether a patient is at risk, the Investigator should obtain appropriate psychiatric consultation prior to releasing the patient.

In the event of a suicide attempt or successful suicide, the investigator will complete a serious adverse events form.

